14.2. Appendix 2: Schedule of Activities

14.2.1. Screening

PROCEDURE	SCREENING PERIOD	NOTES
	Screening may be performed across one or more visits. Part A: up to 28 days before Day 1. Part B: from Day -42 to Day -5 (up to 42 days before Day 1)	
Informed consent	X	,
Inclusion and exclusion criteria	X	
Demography	X	
Full physical examination	X	
Medical/medication/drug/alcohol history	X	
Alcohol and tobacco screens	X	As per standard local practice. Smoking permitted only in Part B.
Urine drug screen	X	
HIV, Hepatitis B (HBsAg and HBcAb) and Hepatitis C (HepC antibody) screening	X	
Holter monitoring	X	24 hour for Part B only
12-lead ECG	Triuplicate	
Vital signs	X	See SRM for details
Echocardiogram	X	
Haematology, clinical chemistry, urinalysis	X	Refer to Appendix 2. C3, C4 and BNP are included.
COVID-19 (SARS-CoV-2)	X	Documented negative COVID test within two days of initial screening OR test performed at the time of initial screening
TB Screening (QuantiFERON)	X	
FSH and estradiol (in WNCBP)	X	
Height and weight	X	
X-ray (K&L of index knee joint)	Part B	Inclusion Criterium. X ray performed only if ALL other inclusion and exclusion criteria were already met at initial screening (except NRS). Allow at least 7 calendar days for the X-ray result to be returned from central reading.
Daily pain scores (Digital Tool)	Part B (Day -7 to Day -1)	Scores will be recorded over the 7 consecutive evenings preceding dosing. Average result (Baseline value) will be evaluated for inclusion.
SAE assessment	X	From signing consent

14.2.2. Part A Cohorts Without Blister: 0.1 and 0.3 mg/kg IV

Procedure	Day												Early withdrawal	Notes
	-1	1	2	3	8	15	22	29	43	57	85	113		
Out-patient visit					X	X	X	X	X	X	X ¹	X ²	X	Allowed visit windows are detailed in the SRM
Admission in clinical unit	X													¹ Final follow-up visit for 0.1 mg/kg cohort ² Final follow-up visit for 0.3 mg/kg cohort
Discharge from clinical unit				X										
Inclusion and exclusion criteria	X													
Brief physical examination	X	X	X	X	X	X	X	X	X	X	X	X		
Alcohol and tobacco screens	X													As per standard local practice
Urine drug screen	X													
Cardiac telemetry		X												Telemetry from at least 12 hrs before dosing until 12hrs post dose. Output to be reviewed for abnormalities prior to dosing on Day 1.
12-lead ECG	Triuplicate	X ¹	X	X	X	X	X	X	X	X	X	X	X	On day -1 and day 1 ECGs may be generated from telemetry ¹ On Day 1, pre dose then every 30 mins during infusion (i.e. 30 mins and 60mins after start of infusion) and then 1 hr post end of infusion.
Vital signs	X	X ¹	X	X	X	X	X	X	X	X	X	X	X	¹ On Day 1, pre dose then every 15 mins during infusion (i.e. 15, 30, 45 and 60mins post the start of infusion) and then 30 mins, 1, 2 and 4 hr post end of infusion.
Haematology, clinical chemistry, urinalysis	X		24hr post dose	48hr post dose	X	X	X	X	X	X	X	X	X	
Weight	X													Weight to be used to calculate the study treatment dose.
Randomization		Pre-dose												
CCI														
Study treatment dosing		X												
AE assessment		<	-----	-----	-----	-----	-----	-----	-----	-----	-----	-----	X	
SAE assessment		<	-----	-----	-----	-----	-----	-----	-----	-----	-----	-----	X	
Concomitant medication review		<	-----	-----	-----	-----	-----	-----	-----	-----	-----	-----	X	

14.2.3. Part A Cohorts With Blister: 1 mg/kg IV

Procedure	Day												Early withdrawal	Notes	
	-1	1	2	3	7	8	15	22	29	42	43	57	85	113	
Out-patient visit							X	X	X			X	X	X	
Admission in clinical unit	X				X					X					
Discharge from clinical unit					X	X					X				
Inclusion and exclusion criteria	X														
Brief physical examination	X	X	X	X	X		X	X	X	X	X	X	X	X	
Alcohol and tobacco screens	X														As per standard local practice
Urine drug screen	X														
Cardiac telemetry		X													Telemetry from at least 12 hrs before dosing until 12hrs post dose. Review for abnormalities prior to dosing on Day 1.
12-lead ECG	Triplet	X ²	X	X	X		X	X	X	X	X	X	X	X	On Day -1 and Day 1 ECGs may be generated from telemetry
															² On Day 1, pre dose then every 30 mins during infusion (i.e. 30 mins and 60mins after start of infusion) and then 1 hr post end of infusion.
Vital signs	X	X ³	X	X	X		X	X	X	X	X	X	X	X	³ On Day 1, pre dose then every 15 mins during infusion (i.e. 15, 30, 45 and 60mins post the start of infusion) and then 30 mins, 1, 2 and 4 hr post end of infusion.
Haematology, clinical chemistry, urinalysis	X		24hr	48hr	X		X	X	X	X	X	X	X	X	
Weight	X														Weight to be used to calculate the study treatment dose.
Randomization		Pre-dose													
Induction of blister	X				X				X						
Aspiration of blister fluid	X					X				X					Aspiration 21 hours (+/- 3 hours) after induction of blister.
Blood sample for circulating immune cells	X					X				X					Cohort 3 only (not needed for Cohorts 1 and 2)
PK blood sample		X	24hr post dose	48hr post dose		X	X	X	X	X	X	X	X	X	D1 Samples to be taken at IV cohorts - pre-dose, 2 hr, 4 hr, 8 hr, and 12 hr post dose SC cohort - pre-dose and 8 hr post dose
CCI															
Study treatment dosing		X													
AE assessment			<-----										X		
SAE assessment			<-----										X		
Concomitant medication review			<-----										X		

14.2.4. Part A Cohorts With Blister: 3 and 10 mg/kg IV and SC

Procedure	Day													Early withdrawal	Notes	
	-1	1	2	3	7	8	15	22	28	29	43	57	85	113	141	
Out-patient visit							X	X		X	X	X	X ¹	X ²	X	Allowed visit windows are detailed in the SRM
Admission in clinical unit	X				X				X							¹ Final follow-up visit for 3 mg/kg IV cohort
Discharge from clinical unit				X	X				X							² Final follow-up visit for 10 mg/kg IV and SC cohorts
Inclusion and exclusion criteria	X															
Brief physical examination	X	X	X	X	X	X	X	X	X	X	X	X	X	X	X	
Alcohol and tobacco screens	X															As per standard local practice
Urine drug screen	X															
Cardiac telemetry		X														Telemetry from at least 12 hrs before dosing until 12hrs post dose. Review for abnormalities prior to dosing on Day 1.
12-lead ECG	Tripletate	X ^{1,2}	X	X	X		X	X	X	X	X	X	X	X	X	On Day -1 and Day 1 ECGs may be generated from telemetry
																¹ On Day 1, pre dose then every 30 mins during infusion (i.e. 30 mins and 60mins after start of infusion) and then 1 hr post end of infusion. ² On Day 1, pre dose then 1 hr post injection.
Vital signs	X	X ^{1,2}	X	X	X		X	X	X	X	X	X	X	X	X	¹ On Day 1, pre dose then every 15 mins during infusion (i.e. 15, 30, 45 and 60mins post the start of infusion) and then 30 mins, 1, 2 and 4 hr post end of infusion. ² On Day 1, pre dose then 1 hr post injection.
Haematology, clinical chemistry, urinalysis	X		24hr p.d.	24hr p.d.	X		X	X	X	X	X	X	X	X	X	
Weight	X															Weight to be used to calculate the study treatment dose.
Randomization		Pre-dose														
Induction of blister	X				X			X								
Aspiration of blister fluid	X					X			X							Aspiration 21 hours (+/- 3 hours) after induction of blister.
Blood sample for circulating immune cells	X					X			X							
CCI																
Study treatment dosing		X														
AE assessment																
SAE assessment																
Concomitant medication review																

14.2.5. Part B

PROCEDURE	SCREEN	a TREATMENT PERIOD (8 Wks)													b FOLLOW-UP (*12 Wks)						See two footnotes. NOTES a) Treatment Period = Day 1 to 57. b) Follow-Up Period = Day 57 to 141. c) Day 141 (End of Study Visit) is ~13 wks since last dose on Day 50.	
		1	2	5	8	15	22	23	26	29	36	43	50	51	57	71	85	99	120	c141		
DAY	Day -4 ¹																					
Out-patient visit	X	X	X	X	X	X	X	X	X	X	X	X	X	X	X	X	X	X	Tel.	X	X	
Discharge from clinical unit		X ¹		X ²	X ²	X ²			X ²	X ²	X ²	X ²										
Inc. & Exc Criteria	X	X																				
Brief Phys. Exam.	X	(X)	X	X	X	X	X	X	X	X	X	X	X	X	X	X	X	X	X	X		
Alcohol and drug screen	X	X		X	X	X			X	X	X	X										
12-lead ECG (Triplicate)	X	(X) ¹	X	X ¹	X ¹	X ¹			X ¹	X ¹	X ¹	X ¹			X	X						
Vital signs	X	(X) ¹	X	X ²	X ²	X ²			X ²	X ²	X ²	X ²			X	X	X					
Haematology, clinical chemistry, urinalysis	(X) ^{1,2}		X	X	X	X			X	X	X	X		X ²	X	X	X					
SARS-CoV-2 PCR Mandatory	X ¹														X							
SARS-CoV-2 PCR Optional				← ¹			← ¹															
Daily Pain (Digital Tool)	See Screen	<----- Daily Pain ----->																			N.B. Pain recorded daily using a digital tool (Evenings of Day 1 to Day 84)	
WOMAC		(X)		X	X				X	X				X	X	X	X	X	X ²		WOMAC, PtGA (participant) & PhGA (Physician Global Assessments) completed prior to ALL other assessments and blood draws. 1) If withdrawal occurs earlier than Day 85.	
PtGA & PhGA		(X)		X	X	X			X	X	X	X		X	X	X	X	X	X ¹			
Pain Detect (Digital Tool)		(X)												X		X					Perform PainDetect after completing WOMAC/Patient & Physician Global Assessment.	
Randomization	X																					
Dosing (SC injections)	X		X	X	X				X	X	X	X									Allow at least 1 hour to thaw vials at room temp (or thaw 18 hours overnight at 2-8°C).	

Concom. Medns	<----->													X							
Trial Questionnaire	(X)	<----->													X	X	Optional trial-based questionnaire for participant completion.				

All activities and blood samples are to be acquired *prior to dosing* (on dosing days), unless stated otherwise.

(X) denotes the Baseline Value.

14.3. Appendix 3: Assessment Windows

Acceptable time windows around the nominal time points for specific assessments will be included in the Study Reference Manual (SRM) and assessments performed within these time windows will not constitute a protocol deviation.

The table below describes the visit days for each week (Week 1-12). All available diary data in each of the weekly intervals will be used to calculate the Average Knee Pain Intensity, Worst Knee Pain Intensity and ^{CCI} [REDACTED] for that study week.

Study Week	Study Day	Phase
BL	-7 to -1	Baseline
1	1 to 7	Treatment
2	8 to 14	Treatment
3	15 to 21	Treatment
4	22 to 28	Treatment
5	29 to 35	Treatment
6	36 to 42	Treatment
7	43 to 49	Treatment
8	50 to 56	Treatment
9	57 to 63	Follow-up*
10	64 to 70	Follow-up
11	71 to 77	Follow-up
12	78 to 84	Follow-up

*Follow-up here means that the participant is no longer receiving the study medication/placebo, so only for informative purposes. Participants will be considered on treatment during the whole duration of the study (20 weeks).

All other assessments will use the nominal timepoints unless otherwise specified.

14.4. Appendix 4: Study Phases and Treatment Emergent Adverse Events

14.4.1. Study Phases

Assessments and events will be classified according to the time of occurrence relative to the first dose.

Study Phase	Definition
Pre-Treatment	Date/time < Study Treatment Start Date/time
On-Treatment	Study Treatment Start Date \leq Date/time

Refer SOA in [Appendix 2](#) for details of follow-up for each Cohort and Part.

14.4.1.1. Study Phases for Concomitant Medication

Study Phase	Definition
Prior	If medication end date is not missing and is >7 days prior to first dose.
Concomitant	Any medication that is not a prior

NOTE: Refer to [Appendix 7](#): Reporting Standards for Missing Data for handling of missing and partial dates for concomitant medication. Use the rules in this table if concomitant medication date is completely missing

In addition, the following phase will also be calculated:

Study Phase	Definition
Prohibited Medication Phase	If medication has start date on or before Day 71 and is either ongoing or has end date on or after 7 days prior to first dose (Section 6.6 of the Protocol)

14.4.2. Treatment Emergent Flag for Adverse Events

Flag	Definition
Treatment Emergent	If AE start date \geq Study Treatment Start Date

NOTES:

- Time of study treatment dosing and start/stop time of AEs should be considered, if collected.

14.5. Appendix 5: Data Display Standards & Handling Conventions

14.5.1. Reporting Process

Software	
The currently supported versions of SAS software will be used.	
Reporting Area	
HARP Server	UK1SALX00175
HARP Compound	\arprod\gsk3858279\mid207804
Analysis Datasets	
Analysis datasets will be created according to Legacy GSK A&R dataset standards	
Generation of RTF and PDF Files	
RTF and PDF files will be generated.	

14.5.2. Reporting Standards

General	

 • The current GSK Integrated Data Standards Library (IDSL) will be applied for reporting, unless otherwise stated: 
 ◦ 4.03 to 4.23: General Principles ◦ 5.01 to 5.08: Principles Related to Data Listings ◦ 6.01 to 6.11: Principles Related to Summary Tables ◦ 7.01 to 7.13: Principles Related to Graphics • All data displays (Tables, Figures & Listings) will use the term “Subject” which reflects CDISC and GSK Data Display Standards terminology. 	
Formats	

 • GSK IDSL Statistical Principles (5.03 & 6.06.3) for decimal places (DPs) will be adopted for reporting of data based on the raw data collected, unless otherwise stated. • Numeric data will be reported at the precision collected on the eCRF. • The reported precision from non eCRF sources will follow the IDSL statistical principles but may be adjusted to a clinically interpretable number of DP's. 	
Actual values will be used in listings. The following criteria will be used in tables and figures:	

 • For all Biomarkers , the following precision places will be applied: 
 ◦ Summary Statistics: 4 significant figures for Mean and Median, 5 significant figures for SD, 3 significant figures for Min and Max, in all cases but Blister Volume parameter. ◦ For Blister Volume parameter: 2DP's, 3 DP's for Mean and Median, 4 DP's for SD, 3 DP's for Min and Max • For PD endpoints, which are blinded until DBF, determination of an appropriate presentation of significant figures will be made after unblinding in line with the IDSL principles 	
Planned and Actual Time	

 • Reporting for tables, figures and formal statistical analyses: 
 ◦ Planned time relative to the first dosing will be used in figures, summaries and planned time relative to the last dosing will be used in statistical analyses and calculation of any derived parameters, unless otherwise stated. ◦ The impact of any major deviation from the planned assessment times and/or scheduled visit days on the analyses and interpretation of the results will be assessed as appropriate. • Reporting for Data Listings: 
 ◦ Planned and actual time relative to study drug dosing will be shown in listings (Refer to IDSL Statistical Principle 5.05.1). ◦ Unscheduled or unplanned readings will be presented within the subject's listings. 	
Unscheduled Visits	

 • Unscheduled visits will not be included in by-visit summary tables and figures. • All unscheduled visits will be included in listings and determination of worst-case values. 	
Descriptive Summary Statistics	
Continuous Data	Refer to IDSL Statistical Principle 6.06.1 – do not report 95% CI unless otherwise specified.
Categorical Data	N, n, frequency, %
Graphical Displays	

 • Refer to IDSL Statistical Principals 7.01 to 7.13. 	

[figure not shown]
14.5.3. Reporting Standards for Pharmacokinetic

Pharmacokinetic Concentration Data	
PC Windows Non-Linear (WNL) File	PC WNL file (CSV format) for the non compartmental analysis by Clinical Pharmacology Modelling and Simulation function will be created according to VQD-GUI-000722 (6.0). Note: Concentration values will be imputed as per VQD-GUI-000722 (6.0).
Descriptive Summary Statistics, Graphical Displays and Listings	Refer to IDSL PK Display Standards. Refer to IDSL Statistical Principle 6.06.1. Note: Concentration values will be imputed as per VQD-GUI-000722 (6.0) for descriptive summary statistics/analysis and summarized graphical displays only.
NONMEM/PK/TE/PD File	PK/TE/PD file (CSV format) for the PK/TE/PD analysis by Clinical Pharmacology Modelling and Simulation function will be created according to the data specification detailed in Section 11.1 Pharmacokinetic / ^{CCI} [REDACTED] / Pharmacodynamic Dataset Specification.
Pharmacokinetic Parameter Derivation	
PK Parameter to be Derived by CPMS	All PK parameters described in Section 9.1.1.2 (Part A and Part B).
PK Parameter to be Derived by Programmer	The following PK parameters will be derived by programmer for Part A: 
 Within subject and timepoint blister fluid: serum concentration ratio for GSK3858279.
Pharmacokinetic Parameter Data	
Is NQ impacted PK Parameters Rule Being Followed	Yes, refer to SOP_314000.
Descriptive Summary Statistics, Graphical Displays and Listings	Refer to IDSL PK Display Standards. Refer to VQD-GUI-000722 (6.0).

CONFIDENTIAL

207804

CCI

14.6. Appendix 6: Derived and Transformed Data

14.6.1. General

Subject Number

 Participants will be assigned a unique identification number: study number concatenated subject ID number. In the case of a subject being enrolled multiple times, the first subject ID number will be used. For more details, see the AR data set specifications. Listings will include both subject ID and unique subject ID.
Multiple measurements at one analysis time point

 Mean of the measurements will be calculated and used in any derivation of summary statistics but if listed, all data will be presented. Participants having both high and low values for Normal Ranges at any post-baseline visit for safety parameters will be counted in both the High and Low categories of "Any visit post-baseline" row of related summary tables. This will also be applicable to relevant Potential Clinical Importance summary tables.
Study day

 Calculated as the number of days from first dose date: 
 ref date = missing → study day = missing ref date < first dose date → study day = ref date – first dose date ref date ≥ first dose date → study day = ref date – (first dose date) + 1
Nominal Visit Day

 Nominal Visit Days were updated in protocol, however some visits may be recorded under the incorrect visit number/label for Part A only: 
 Day 112 and Day 113 will be collapsed under the Nominal Visit: Day 113. Day 140 and Day 141 will be collapsed under the Nominal Visit: Day 141.

14.6.2. Study Population

Age

 • Birth date will be presented in listings as 'YYYY'. • GSK standard IDSL algorithms will be used for calculating age where birth date will be imputed as follows: 
 ◦ Any participant with a missing day will have this imputed as day '15'. ◦ Any participant with a missing date and month will have this imputed as '30th June'. • Calculated based on the screening date
Body Mass Index (BMI)

 • Calculated as Weight (kg) / [Height (m)²]
Race Category

 • The five high level FDA race categories and designated Asian subcategories will be summarised along with all combinations of high level categories which exist in the data. • The high level FDA race categories and designated Asian subcategories are: 
 ◦ AMERICAN INDIAN OR ALASKA NATIVE ◦ ASIAN 
 ◦ CENTRAL/SOUTH ASIAN HERITAGE ◦ JAPANESE HERITAGE/EAST ASIAN HERITAGE/SOUTH EAST ASIAN HERITAGE ◦ MIXED ASIAN RACE (only required if data exists) ◦ BLACK OR AFRICAN AMERICAN ◦ NATIVE HAWAIIAN OR OTHER PACIFIC ISLANDER ◦ WHITE • A subject who selects a combination of races will be counted in a row within "MULTIPLE" or within the "MIXED ASIAN RACE", not in each of the constituent terms.
Extent of Exposure

 • Number of days of exposure to study drug in Part B will be calculated based on the formula: 
 ◦ Duration of Exposure in Days = Treatment Stop Date – (Treatment Start Date) + 1+18*5 ◦ Note: The half life of the drug is approximately 18 days. Hence 5*18 =~ 90 days is added in the equation of duration of exposure. • Participants who were randomized but did not report a treatment start date will be categorised as having zero days of exposure. • The summary statistics based on the frequency of injections would be provided in the exposure display for Part B.

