4.1.1. Treatment Groups and Duration

The total duration of the study (from signing of the informed consent until final follow-up) for each participant will vary between cohorts (see Table 1). The screening period will be of a maximum of 28 days for all cohorts in Part A and a maximum of 42 days in Part B. Final follow-up visits will be scheduled to occur when approximately 5 half-lives of GSK3858279 have elapsed after dosing. Follow-up visits are scheduled earlier for the lowest dose group where PK parameters are expected to be below the lower limit of quantification (LLQ), and are extended by an additional 4 weeks for the top dose cohort where extended pharmacology may be observed (see Table 1 and Schedule of Activities [SoA, Section 1.3]).

In Part A, each participant will receive a single dose of study intervention (GSK3858279 or placebo), either IV or SC. The planned dosing schedule is described in Table 1, although dose levels are subject to change depending on emerging study data. The maximum dose (level) that may be administered in the study will be 10 mg/kg, both for IV and SC cohorts. See Section 4.4 for further details.

In Part B, each participant will receive SC injections weekly for 8 weeks.

Table 1 Dosing schedule and study duration

Part	Cohort	Dose of GSK3858279	Follow up (days post dosing)	Maximum study duration including screening (days)
Part A	Cohort 1 IV	Up to 0.1 mg/kg	84	112
	Cohort 2 IV	Up to 0.3 mg/kg	112	140
	Cohort 3 IV	Up to 1 mg/kg	112	140
	Cohort 4 IV	Up to 3 mg/kg	112	140
	Cohort 5 IV	Up to 10 mg/kg	140	168
Cohort 6 SC	Between 1 and 3	140	168	
	Colloit 6 SC	mg/kg (max 240 mg)		
Part B	Cohort 7 SC	240 mg	56 (Treatment)	182/183
			84(Follow Up)	

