6.1. Study Intervention(s) Administered

Study intervention is defined as any product received by the participant as per the study protocol. Study intervention may therefore refer to GSK3858279 or placebo.

Table 3 Study interventions

Product name:	GSK3858279	Diluent/Placebo
Formulation description:	GSK3858279 is formulated in 0.79 mg/mL sodium acetate, 50 mg/mL sorbitol, 0.4 mg/mL polysorbate 20, glacial acetic acid 0.28 mg/mL, water for injection, pH 5.0. GSK3858279 contains no preservative.	Normal Saline (0.9% sodium chloride)
Dosage form:	Solution for injection	Solution for injection
Unit dose level:	50 mg/mL. Each vial has an extractable volume of 3.0 mL (150 mg per vial).	0.9% w/v sodium chloride, placebo level variable.
Route of administration and duration:	IV or SC	IV or SC
Dosing instructions:	IV cohorts 1-5: GSK3858279 will be infused over up to 1 hour. GSK3858279 can be diluted in normal saline prior to administration. SC Cohorts 6 (Part A) ¹ and 7 (Part B) ² The appropriate volume of GSK3858279 will be injected using a syringe at	The appropriate volume of normal saline will be infused (IV) or injected (SC) in the same manner as the corresponding active cohort.

	no more than 1.2 mL per injection.	
Physical description:	The drug product is a brown to yellow solution stored in 5 mL glass vials with a 20 mm rubber stopper and a grey-brown 20 mm Flip-top aluminium overseal.	Commercial presentation
Manufacturer/source of procurement:	Study medication is supplied by GSK.	0.9% w/v sodium chloride is sourced locally by the site.

¹⁾ Part A: As a maximum of 4 SC injections will be administered for feasibility reasons, the maximum dose that will be administered to participants weighing >80 kg will be 240 mg.
2) For Part B, all participants are to receive a weekly dose of 240 mg SC (4 x 1.2 mL injections) irrespective of weight.

The doses of GSK3858279 for injection will be prepared at the clinical site by an unblinded pharmacist from the stock solution provided (see Table 3).

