14.11.6.2. Part B

No.	Population	IDSL / Example Shell	Title	Programming Notes	Deliverable
Subject Disposition					
1.10.	Randomized	ES1	Part B: Summary of Subject Disposition for the Subject Conclusion Record		IA1, IA2, IA3, IA4, Part B SAC
1.11.	Randomized	SD1	Part B: Summary of Treatment Status and Reasons for Discontinuation of Study Treatment		IA1, IA2, IA3, IA4, Part B SAC
1.12.	Screened	ES6	Part B: Summary of Screening Status and Reasons for Screen Failure		Part B SAC
1.13.	Enrolled	NS1	Part B: Summary of Number of Subjects by Country and Site ID		Part B SAC
COVID-19					
1.14.	Randomized	PAN1A	Part B: COVID-19 Case Diagnosis Events		Part B SAC
Protocol Deviation					
1.15.	Randomized	DV1	Part B: Summary of Important Protocol Deviations		Part B SAC
Population Analysed					
1.16.	Screened	SP1	Part B: Summary of Study Populations	Include footnote with population definitions.	Part B SAC
Demographic and Baseline Characteristics					
1.17.	Randomized	DM1	Part B: Summary of Demographic Characteristics	ICH E3, FDAAA, EudraCT Include KL scores	IA1, IA2, IA3, IA4, Part B SAC
1.18.	Randomized	POP_T1	Part B: Summary of Baseline Efficacy Parameters	Include Average & Worst Knee Pain Intensity, WOMAC, ^{CCI} [REDACTED] [REDACTED] and Pain Detect	IA1, IA2, IA3, IA4, Part B SAC

CONFIDENTIAL

207804

No.	Population	IDS / Example Shell	Title	Programming Notes	Deliverable
1.19.	Enrolled	DM11	Part B: Summary of Age Ranges	EudraCT	Part B SAC
1.20.	Randomized	DM5	Part B: Summary of Race and Racial Combinations	ICH E3, FDA, FDAAA, EudraCT	Part B SAC
Medical Conditions					
1.21.	Randomized	MH4	Part B: Summary of Past Medical Conditions	ICH E3	Part B SAC
1.22.	Randomized	MH4	Part B: Summary of Current Medical Conditions	ICH E3	Part B SAC
Prior and Concomitant Medications					
1.23.	Safety	CM1	Part B: Summary of Prior Medications	ICH E3	Part B SAC
1.24.	Safety	CM1	Part B: Summary of Concomitant Medications	ICH E3	Part B SAC
1.25.	Safety	CM1	Part B: Summary of Prior Osteoarthritis Medications	OA meds are captured on a specific CRF page	Part B SAC
1.26.	Safety	CM1	Part B: Summary of Osteoarthritis Concomitant Medications during Prohibited Medication Phase		Part B SAC
1.27.	Safety	CM1	Part B: Summary of Osteoarthritis Concomitant Medications		Part B SAC
Exposure					
1.28.	Safety	EX1	Part B: Summary of Exposure to Study Treatment	Provide statistics for the categories by number of injections received (4 injections, ≤ 3 injections)	Part B SAC

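### The Part B exposure figure adds 90 days for every dosed participant, placebo included, and Table 1.28 specifies no count of the eight weekly doses received

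*SAP*

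**What the plan says.** SAP 14.6.2 (Extent of Exposure) defines the number of days exposed to study drug in Part B as "Duration of Exposure in Days = Treatment Stop Date – (Treatment Start Date) + 1+18*5". It gives the reason: the half-life is about 18 days, and "Hence 5*18 =~ 90 days is added in the equation of duration of exposure". There is one exception: "Participants who were randomized but did not report a treatment start date will be categorised as having zero days of exposure". The section then adds that "The summary statistics based on the frequency of injections would be provided in the exposure display for Part B".

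The display is Table 1.28 in SAP 14.11.6.2, on the Safety population with standard shell EX1. Its programming note reads "Provide statistics for the categories by number of injections received (4 injections, ≤ 3 injections". The Safety population (SAP 4.1.1) is everyone randomized who had at least one dose, in either arm.

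Protocol 6.1, Table 3, footnote 2 sets the dose: "For Part B, all participants are to receive a weekly dose of 240 mg SC (4 x 1.2 mL injections) irrespective of weight". The same table gives normal saline as the placebo, injected in the same way as the active product. Protocol 4.1.1 gives the course: "In Part B, each participant will receive SC injections weekly for 8 weeks". The Part B schedule has dosing on Days 1, 8, 15, 22, 29, 36, 43 and 50, and the end-of-study visit on Day 141.

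**The concern.** The formula depends only on the first and last dosing dates, plus a constant. Three things follow.

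- **Placebo.** A drug half-life has no meaning for saline, yet placebo participants are reported with the same 90 days. If study drug is read to include placebo injections, the washout term still has nothing to refer to.
- **Early leavers and missed doses.** The constant dominates short courses, so someone who stopped after one dose looks much closer to a completer than they were. Protocol 7.2.4 allows the investigator to withhold a dose, and a skipped mid-course dose leaves the figure unchanged.
- **No offsetting dose count.** The injection categories in the table note top out at one week's dose.

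Safety is a primary objective of Part B, which is the first repeat dosing in this first-in-human study. A reader of the safety results needs to see how much treatment each arm received, and the table as specified blurs that.

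**Working it through.** **Inputs.** Half-life about 18 days and the formula: SAP 14.6.2. Dosing days and end of study: Part B schedule (Protocol 1.3.5, SAP 14.2.5). Four injections per weekly dose: Protocol 6.1. I take the treatment stop date as the date of the last dose; SAP 14.6.2 does not define it.

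**The plan's own figure.** 5 × 18 = 90 days, as stated.

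**The formula at selected last-dose days.** SAP days = (last − first + 1) + 90.

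| Doses received | Last dose day | Dosing days | SAP days | SAP days as % of full course | Doses as % of full course | Cumulative injections |
|---|---|---|---|---|---|---|
| 1 | 1 | 1 | 91 | 65% | 12.5% | 4 |
| 2 | 8 | 8 | 98 | 70% | 25% | 8 |
| 4 | 22 | 22 | 112 | 80% | 50% | 16 |
| 6 | 36 | 36 | 126 | 90% | 75% | 24 |
| 8 | 50 | 50 | 140 | 100% | 100% | 32 |

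For example, one dose gives 1 − 1 + 1 + 90 = 91, and 91/140 = 65%. The constant is 90/91 = 98.9% of the one-dose figure and 90/140 = 64.3% of the full-course figure. The rule has no arm condition, so the same 91 to 140 days apply to placebo.

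**Missed dose.** Seven doses with one mid-course dose withheld: 50 − 1 + 1 + 90 = 140, identical to a full course.

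**Time observed.** For a completer, 140 days fits inside the Day 141 visit. For illustration, a participant with one dose and last contact on Day 10 would be reported with 91 days, 91 − 10 = 81 more than were observed.

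**Injection categories.** Read as totals over the course, 4 and ≤3 leave 5 to 32 injections without a category (8 × 4 = 32). Read per dosing visit, they show whether each weekly dose was complete, but not how many doses were given. The note does not say which reading applies, and neither yields a count of doses from 1 to 8.

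**Without the 90 days.** Dosing duration runs from 1 day (one dose) to 50 days (eight doses), or 7 to 56 days if each dose is credited with its 7-day interval.

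**The case against.** The strongest reply is that the 90 days are a declared definition and fit the design. Protocol 4.1.1 schedules final follow-up at about five half-lives; Day 50 to Day 141 is 91 days, or 91/18 = 5.06 half-lives. SAP 14.3 counts participants as on treatment for 20 weeks, exactly the completer's 140 days. SAP 14.4 counts adverse events from first dose with no end date, so a 50-day figure alone would sit beside events gathered over 20 weeks. An antibody with an 18-day half-life also does not vanish when a participant stops dosing. For the active arm this stands: the allowance is pharmacologically reasoned, not an arithmetic error. It supports showing the figure under its own label, not merging it with treatment received.

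A second reply is that one rule for both arms keeps them comparable. The absolute difference is indeed preserved, but the ratio is not: eight against four doses is 140/112 = 1.25 on the SAP scale and 50/22 = 2.27 in dosing days.

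A third is that participants withdrawn from treatment should, where possible, be followed for safety (Protocol 7.2), so a very short observation time may be uncommon. That limits how often the figure exceeds time observed. It does not supply a cap, and Protocol 7.3 lets participants leave at any time.

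A reader might also infer that the report cannot show doses received. The documents do not support that. SAP 14.6.2 promises injection statistics in the display, Listing 46 includes the number of injections, Table 1.11 covers treatment discontinuation, and the EX1 shell is not in the documents, so its default rows are unknown.

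**Conclusion.** The point holds as a definition and labelling fault in one descriptive table. The rule gives placebo participants 91 to 140 days of drug exposure they did not have. It shows one of eight doses as 65% of a full course, can exceed the time observed, and does not register a missed mid-course dose. Table 1.28's note, as it stands, does not ask for the number of doses received.

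Two limits apply. The 90 days do not reach everyone randomized: a participant with no treatment start date gets zero. And although a reader might take the table as the denominator for adverse event rates, the Part B safety tables listed in the SAP are summaries by subject and occurrence, and no exposure-adjusted rate is specified. No adverse event result, efficacy analysis or interim decision changes.

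The sizes assume dosing on the planned days and a stop date equal to the last dose date. Visit windows would move them by a day or so. The importance is minor.

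**What to change.** In SAP 14.6.2 and Table 1.28:

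1. Report, by arm, the number of weekly doses received (1 to 8).
2. Report dosing duration without the 90 days, defining the stop date and saying whether the last dose is credited with its 7-day interval. SAP 7.1.4 already uses last dose + 7 days to date treatment withdrawal.
3. If a five-half-life figure is wanted, show it as a separately labelled item for the active arm only.
4. If follow-up time is shown, cap it at last contact in both arms.
5. State that the 4 and ≤3 injection categories are per dosing visit.

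The cost is a wording change and one re-programmed table. No new data are needed: Listing 46 already carries injection counts, and the Per Protocol rule in SAP 14.1.1 (more than 1 of 8 doses missed) already requires doses to be counted. The downside is that the stated exposure becomes smaller.
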